**c. Justification and safety information if non-FDA approved drugs without an IND will be administered.**

Fat is stored in adipose tissue as triglycerides, which are comprised of glycerol and fatty acids. Measurement of glycerol and fatty acid levels in plasma does not provide information about the turnover rate or flux of these substances through the body. To assess these dynamic parameters requires administration of isotopes. Stable isotopes have been used safely for decades of metabolic research. Stable isotopes are not radioactive and occur in nature. A small percentage of the body's glycerol, fatty acids, and water already exist as stable isotopes. In this study we will temporarily increase the amount of these isotopes to tracer levels that can only be detected by a mass spectrometer.

In terms of safety, our infusates will be prepared with the Johns Hopkins Research Pharmacy under sterile conditions. The FDA's policy on stable isotopes states that if substance would not otherwise require submission of an IND, then that substance enriched with a stable isotope will not require an IND. If the isotope enrichment is for metabolic tracer studies employing drugs or non-pharmacological substances, such as glucose and individual amino acids, for which there are adequate data demonstrating their safety and if the substances are used within the limits for which the data are adequate, no IND will be required. The exemption information has been separately uploaded in the IRB application.

**7. Study Statistics**

- a. Primary outcome variable: Nocturnal FFA and glucose profile
- b. Secondary outcome variables: Morning EndoPAT, lipid panel. Sleep study parameters (e.g. total sleep time, latency, wake after sleep onset, sleep stages, AHI, oximetry, heart rate). Lipid flux data (rate of lipolysis and FFA turnover using stable isotope data; rate of fatty acid oxidation), DNA methylation profile.
- c. Statistical plan including sample size justification and interim data analysis.

**Comparisons between CPAP, [NDS + propranolol], and [NDS + Placebo]:** Primary outcome is comparison of metabolism and blood pressure for [NDS + propranolol] versus [NDS + placebo]. For metabolic parameters that are repeatedly measured during sleep (e.g. FFA, glucose) we will use mixed linear model analysis with experimental group as a fixed factor and subject ID as a random factor. Sleep physiology that is measured on a continuous basis (e.g. heart rate, AHI, SpO2) will be condensed into 30 minute bins to create a parallel data structure with metabolic parameters. We will then examine whether these sleep physiological metrics are dynamically associated with glucose/FFA level. For those parameters that are measured once per visit (e.g. RHI, lipid panel), we will compare using paired T-tests for within-subject comparisons between nights. A secondary outcome is whether CPAP and [NDS + propranolol] are similar, and this will be performed using a similar pairwise comparison. In addition, one way ANOVA will be used to ascertain whether there is a detectable difference across all three groups. Multiple regression will be used to examine associations between FFA, glucose, CPAP status, and drug adjusting for potential confounders such as diabetes, BMI, body fat (DEXA) and age. As an exploratory analysis, Pearson correlation matrices will be used to probe the interrelatedness of glucose, FFA, insulin, lipids, and sleep outcomes, followed by targeted multivariable regression. We plan an analysis of each subject's pulse rate and blood pressure after their PSG to determine whether beta blocker dosage or timing requires adjustment, which will expedite the ability to tailor the therapy if necessary.

An exploratory aim of this study is to examine effects of CPAP withdrawal on peripheral blood mononuclear cell (PBMC) gene expression. We will utilize real-time polymerase chain reaction (RT-PCR) arrays (Qiagen MAP Kinase RT2 Profiler and Human Toll-Like Receptor (TLR) Signaling Pathway RT2 Profiler PCR Arrays, Qiagen, Valencia, CA) to characterize gene changes that result from nocturnal hypoxemia.

**Sample size:** In our preliminary data from 3 patients who have completed their study visits, FFA levels increased with OSA (CPAP withdrawal), and propranolol abolished this response. The mean nocturnal FFA level on CPAP, [OSA + placebo], and [OSA + propranolol] nights was  $0.413 \pm 0.107$ ,  $0.447 \pm 0.084$  and  $0.313 \pm 0.067$  mmol/L respectively. We base our sample size on the ability to detect an effect of propranolol on FFA levels during sleep. The mean difference of FFA between [OSA + placebo] and [OSA + propranolol] nights was  $0.133 \pm 0.076$  mmol/L (mean  $\pm$  standard deviation). This yields a large effect size (Cohen's  $d = 1.673$ ). However, we anticipate a smaller effect size with ongoing enrollment. In addition, our pilot data consisted only of men, and we do not have data from which to estimate an effect size for women. We estimate a more modest difference in means of 0.06. This yields a Cohen's  $d = 0.79$ . To detect a difference at 90% power at a significance level of 0.05 requires a sample size of 15 subjects. We will compare both sexes, so we will target an enrollment of 30 subjects. To account for 20% data loss from technical problems (IV failure, hemolysis, poor sleep efficiency) we will consent 36 subjects.

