**Study overview:** There are a total of 4 study visits. The first visit is a consent, screening, and randomization visit. After consent, a screening EKG will be performed to exclude rhythm or conduction abnormalities and a urine pregnancy test to exclude pregnancy in potentially pregnant females. (If the participant has had a clinical EKG or EKG report in the last year that does not indicate any conduction disorders listed in the exclusion criteria, the screening EKG may be deferred.) A point of care screening test for hemoglobin will also be performed to exclude pre-existing anemia. Patients with a hemoglobin < 10 g/dL are ineligible for this study. They will be provided with ClearPassage® NDS to use at home during CPAP withdrawal nights.

Thereafter, there are 3 overnight visits to the CRU in random order. This protocol compares nocturnal metabolism in treated OSA (CPAP), untreated OSA (NDS), and beta-blocked OSA (NDS) in the same subject. OSA nights are performed in the lab after using NDS instead of CPAP for 2 nights at home.

**Covid-19 screening:** We will screen participants before their arrival for their each sleep study with a Covid-19 test. A negative screen within 72 hours of the CPAP visit will be needed prior to admission for the CPAP study visit.

During each OSA visit, propranolol or placebo is taken in the evening, in random order. Frequent blood sampling is performed throughout the visit. In the morning, DEXA (only 1 DEXA needed for entire study) is performed. We are targeting 1 week between visits, but will allow flexibility in scheduling patients unable to schedule 3 consecutive visits exactly 1 week apart; in this scenario we will allow a duration of  $\geq$  4 days or  $\leq$  3 weeks between visits. Each visit we will also administer stable isotopes to measure detailed lipid metabolism.

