### Data Analysis and Anticipated Outcomes:

The primary outcomes are nocturnal glucose and FFA levels. The main independent variable is experimental condition: [CPAP], [OSA+placebo], or [OSA+propranolol]. Since glucose and FFA are measured multiple times per subject per night, we will perform mixed linear model analysis using condition as a fixed factor and subject ID as a random factor. We will also examine whether there are independent or interacting effects of time, or time x condition on trajectories of FFA and glucose. We hypothesize that OSA increases glucose and FFA levels during [OSA + placebo] nights, compared to [CPAP], or [OSA + placebo] nights. We further hypothesize that propranolol will suppress nocturnal FFA and glucose to levels similar to that of CPAP. Sleep physiology that is measured on a continuous basis will be condensed into 30 minute bins to create a parallel data structure with metabolic parameters. We will then examine whether sleep physiology (e.g. AHI, arousals, heart rate) is dynamically associated with glucose or FFA, and whether urine catecholamine levels are associated with increases in FFA or glucose. For variables measured once (RHI, morning lipid profile) or averaged together (e.g. nocturnal glucose level) we will perform one-way ANOVA for comparisons. We will also compare sleep physiology between the 3 nights, examining variables such as apnea hypopnea index, metrics of hypoxia, and sleep architecture/duration. A questionnaire will be administered each morning to assess subjective sleep quality from the night prior, and to screen for any symptoms related to study medication. These responses will be used to determine how symptomatic a subject's OSA is, whether subjective sleep quality correlates with extent of metabolic change, and whether any side effects of beta blockade were perceived.

Regarding tracer data, we predict that  $R_a$  FFA and  $R_a$  glycerol will exhibit a ~3:1 ratio reflecting typical patterns of lipolysis without significant intra-cellular recycling. Based on studies of normal sleep [39, 40], we predict that on CPAP, sleep reduces lipolysis and FAO compared to wakefulness. During CPAP withdrawal, sleep will increase lipolysis (or at least mitigate sleep-induced suppression) compared to wakefulness. We hypothesize that FAO will be reduced or unchanged by OSA. This pattern of increased lipolysis without increased FAO may lead to

ectopic lipid deposition and extracellular TG cycling (see figure).

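### The protocol's mixed model for nocturnal FFA and glucose has no night-level random term although condition is set once per night, and no text says the SAP's paired analysis replaces it

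*Protocol*

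**What the plan says.** Protocol section 7a names the primary outcome: "Primary outcome variable: Nocturnal FFA and glucose profile". For these repeated measurements section 7c states "we will use mixed linear model analysis with experimental group as a fixed factor and subject ID as a random factor". The data-analysis part of section 4 agrees: "we will perform mixed linear model analysis using condition as a fixed factor and subject ID as a random factor". It adds fixed terms for time: "We will also examine whether there are independent or interacting effects of time, or time x condition on trajectories of FFA and glucose".

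The design is a within-person comparison. Section 4 says "This protocol compares nocturnal metabolism in treated OSA (CPAP), untreated OSA (NDS), and beta-blocked OSA (NDS) in the same subject" and "there are 3 overnight visits to the CRU in random order". Drug or placebo is taken once, in the evening. Blood is drawn every 30 minutes during the sleep study, which runs from 10:30 PM to 6:30 AM.

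For single values per night, section 4 says "For variables measured once (RHI, morning lipid profile) or averaged together (e.g. nocturnal glucose level) we will perform one-way ANOVA for comparisons". Section 7c says of once-per-visit variables "we will compare using paired T-tests for within-subject comparisons between nights", and adds a one-way ANOVA across the three conditions.

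The SAP (25 April 2023) makes median heart rate the primary outcome and lists FFA, glucose and insulin as secondary. Its Analysis section compares one summary per night by paired t-test and applies similar methods to the secondary outcomes. Mixed models appear there only under Exploratory Analyses. The SAP describes a comparison of propranolol with placebo and specifies none with CPAP.

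**The concern.** A person has one night per condition, so the error that matters for a condition contrast is the variation between nights within that person. A subject intercept removes differences between people but leaves this variation in place. With only that intercept, the model treats the samples from one night as separate evidence about condition. Fixed time and time-by-condition terms describe the average curve and do not supply the missing term.

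If this analysis is run, p-values for FFA and glucose can be too small, and these are the protocol's primary outcomes. One-way ANOVA errs the other way: it leaves between-person variance in the error term and can miss a difference that a within-person test would find. Since no text says whether the SAP replaces the protocol's analyses, the FFA and glucose conclusion could depend on which document the analyst follows.

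**Working it through.** **The plan's own figure.** Protocol section 7c sizes FFA on a difference of 0.06 mmol/L and an SD of 0.076, so d = 0.06/0.076 = 0.79, and states 15 subjects for 90% power at 0.05. A paired t-test with n=15 has 89.7% power one-sided and 81.2% two-sided. The stated 15 is therefore reproduced, within rounding, as a one-sided paired test. The sizing thus rests on one paired difference per person, not on a sample-level model.

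**Inputs.** Samples per night: 8 h at 30-minute spacing gives m = 8/0.5 + 1 = 17 (extra draws for the tracer are ignored). Conditions K = 3; n = 15. Night-to-night SD within a person is σn and within-night SD is σe, with r = σn/σe. The documents do not give σe, so r is assumed.

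**Standard error.** With balanced data the subject intercept cancels from a difference between conditions.
- True variance of the difference: 2(σn² + σe²/m)/n = 2(mσn² + σe²)/(nm).
- Variance the model reports: 2·MS/(nm), where the expected MS is σe² + σn²·m(n−1)(K−1)/df and df = nKm − n − K + 1.
- Here df = 765 − 15 − 3 + 1 = 748, and 17·14·2/748 = 0.636.
- True SE / model SE = √[(1 + 17r²)/(1 + 0.636r²)].
- False-positive rate ≈ 2Φ(−1.963/ratio), where 1.963 is the two-sided 5% point of t on 748 df.

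| r (assumed) | (1+17r²)/(1+0.636r²) | SE ratio | False positives, formula | Simulated |
|---|---|---|---|---|
| 0 | 1/1 | 1.00 | 5% | 5% |
| 0.1 | 1.17/1.006 | 1.08 | 7% | 7% |
| 0.25 | 2.06/1.040 | 1.41 | 16% | 16% |
| 0.5 | 5.25/1.159 | 2.13 | 36% | 36% |
| 1.0 | 18/1.636 | 3.32 | 55% | 55% |

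The simulation used 20,000 null trials per row. Separate runs gave 35% at r = 0.5 and 56% at r = 1.0, which is Monte Carlo agreement. A paired t-test on nightly means stayed at about 5% in every row. The ratio is scale-free, so the table applies to glucose as well as FFA.

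**Check with a fitted model.** Actual mixed-model fits (150 runs, n=15, paired SD 0.076, within-night SD 0.10) rejected 33% with a subject intercept only and 6% once a subject-by-night component was added.

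**In FFA units.** Suppose 0.076 is the SD of the paired difference of nightly means. Then σn² = 0.076²/2 − σe²/17. For assumed σe of 0.05, 0.10, 0.15 and 0.20 mmol/L the rate is 57%, 35%, 18% and 8%; n=16 and n=30 are within 1 point. If FFA also follows an assumed linear overnight trend of ±0.15 and no time term is fitted, as section 7c reads, the rates fall to 32%, 21%, 11% and 5%, because the trend swells the residual. Fitting time, as in section 4, returns them to 56%, 34%, 17% and 8%. The value 0.076 comes from 3 patients. It also equals the pooled SD of the two nights, √((0.084² + 0.067²)/2) = 0.076, so it may not be the SD of the difference. The scale-free table does not depend on it.

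**One-way ANOVA.** Take one condition raised by 0.06, per-night SD 0.076, an assumed within-person correlation of 0.5 and n=15. The squared deviations of the three means sum to 0.06²·2/3 = 0.0024. Repeated-measures ANOVA has error variance 0.076²·(1 − 0.5) = 0.00289 and noncentrality 15·0.0024/0.00289 = 12.5 on 2 and 28 df, giving 86% power. One-way ANOVA on the same data, by simulation, has about 55%. At correlation 0.3 the figures are 55% versus about 72%, and at 0.7 about 54% versus 98%. With no true effect and correlation 0.5, one-way ANOVA rejects 0.5%.

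**The case against.** The strongest reply is that the SAP has largely dealt with this. It makes FFA and glucose secondary, gives them a paired comparison of one summary per night, and moves mixed models to exploratory status. That stands for propranolol versus placebo, and the paired test there is valid. A reader might infer that the documents assign FFA and glucose no governing analysis at all; the SAP contradicts that. What remains is narrower. Nothing says the SAP's test replaces Protocol sections 4 and 7c, and those sections are the only specification for the CPAP and three-condition comparisons.

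A second reply is that naming subject ID as a random factor is shorthand and does not exclude other random terms. That is fair, and the error rates apply only to the literal model. But no other term is named, and the literal model is what an analyst following the text would fit.

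Third, a reader might see a contradiction between the ANOVA in section 4 and the paired t-tests in section 7c for the vascular index and lipids. The documents do not support that strongly, since an overall test and pairwise tests can coexist. A reader might also infer that one-way ANOVA produces false positives. It does not here; it is conservative. The term may even be loose wording for one within-person factor, though neither section says so.

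Fourth, the SAP's exploratory model names a subject effect plus random slopes without saying whether the slope is on drug or on time. A drug slope would cure the fault; a time slope alone would not. The examples given are heart rate, oxygen level and apnea-hypopnea index, so this is an ambiguity in an exploratory model and not a demonstrated error.

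Finally, the size depends on assumed variances. That is correct: the direction is certain whenever nights vary, but the amount is not.

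**Conclusion.** The concern holds in a limited form and should be fixed. Fitted as written, the protocol's mixed model understates the standard error for condition whenever nights vary within a person. At n=15 with 17 samples per night, the false-positive rate is about 7%, 16%, 35% or 55% for assumed night-to-within-night SD ratios of 0.1, 0.25, 0.5 and 1.0, and about 5% if nights do not vary at all. These are conditional figures, not predictions for this trial. Literal one-way ANOVA loses power, about 55% versus 86% in the worked case, and does not inflate error.

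It would go too far to conclude that the trial's main result is at risk. The SAP primary, median heart rate by paired t-test, is unaffected, and the SAP's own test for FFA and glucose is sound for propranolol versus placebo.

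**What to change.** 1. State that the SAP's paired analysis of nightly summaries governs FFA and glucose for propranolol versus placebo, and that it replaces Protocol sections 4 and 7c for that comparison.
2. Add a subject-by-night random effect (equivalently subject-by-condition, as there is one night per condition) to any sample-level model, including the CPAP and three-condition comparisons.
3. In both protocol sections, replace one-way ANOVA with repeated-measures ANOVA with subject as block.
4. Minor: if the SAP's exploratory model is used, have its random slope include drug, or add a night-level term.

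The cost is wording only; no new data are needed. Mixed-model p-values will become less favourable. A drug slope may be hard to fit with about 15 subjects, which is a further reason to let the paired nightly summary carry the conclusion.

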**c. Blinding, including justification for blinding or not blinding the trial, if applicable.**

The subject and investigator will be blinded to whether they receive placebo or propranolol. This will control for the potential placebo effect of taking any medication before sleep. The investigator will unblind the drug assignment after the first 6 completed participants, so that adjustments to propranolol timing or dosage can be performed depending upon hemodynamic and metabolic effects. At that point, if the average OSA-induced FFA level is not reduced by at least 10%, the dosage of Inderal LA will be increased from 80 to 120 mg. The dosage will be reduced if there is any evidence of excessive bradycardia ( $>15\%$  reduction in heart rate) or hypotension (systolic BP $<90$ ). In addition, if the FFA nadir does not occur during the main sleep period, the timing of propranolol administration will be advanced or delayed as necessary. These adjustments will be made in collaboration with the research pharmacy. Regardless of whether the PI is blinded or unblinded, all data collection (sleep study, EndoPAT etc) will be performed in a blinded manner. For CPAP withdrawal nights, NDS will be used as a CPAP placebo. This will control for unintended effects of stopping CPAP such as anxiety before sleep.

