Propranolol for Sleep Apnea Treatment (PROSAT)

NCT03049306

April 25, 2023

PROPRANOLOL FOR SLEEP APNEA THERAPY (PROSAT)

STATISTICAL PLAN

April 25, 2023

Developed by:

[figure not shown]
[figure not shown]
[name], Division of Pulmonary and Critical Care Medicine

[name], Johns Hopkins School of Public Health

Background:

20 million adults in the United States and >100 million adults worldwide have OSA, and the prevalence continues to rise with obesity. These figures are especially alarming as OSA is associated with cardiovascular disease and mortality. However, mechanisms linking OSA to these outcomes are unclear. As a result of this knowledge gap, fundamental questions such as what features of OSA are most harmful, and which patients can safely decline treatment, cannot be answered. Moreover, therapies for OSA such as CPAP are poorly tolerated, leaving non-adherent patients susceptible to CVD. We have observed that OSA acutely elevates nocturnal heart rate, morning blood pressure, and morning augmentation index (AIX)¹. These short-term changes may foster progression of cardiovascular disease if they recur on a chronic basis. In other contexts, these cardiovascular changes are induced by sympathetic nervous system activation. Therefore, we hypothesize that catecholamine release during sleep leads to increased heart rate, blood pressure, AIX, and altered metabolism. In this project we will examine whether OSA-related cardiometabolic changes during sleep can be prevented by beta blockade.

Design: Double-blind, crossover RCT of Propranolol LA vs. Placebo taken before sleep in patients with moderate-severe OSA. Participants will be CPAP-adherent patients who will temporarily discontinue CPAP for 3 nights prior to each visit, approximately 1 week apart. During sleep we will collect a full sleep study (oximetry, sleep staging, respiratory flow, muscle movements), IV blood samples (every 30 min). In the morning following each study, participants will undergo vascular assessment (endoPAT testing).

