Sample size: In a preliminary study (n=6), Median individual heart rate during sleep \pm (SD) was 62.2 (9.2) with [OSA+placebo] and this decreased by 6.7 BPM with [OSA+propranolol]. To detect a 10% difference (reduction of 6.2 beats/min) at a power of 80% at a significance threshold of 0.05, using a one-tailed comparison, yields a sample size of 16 participants. Since we have already enrolled 5 subjects, we require 11 additional subjects. Assuming 20% dropout, we will enroll 14 additional subjects, a total of 19 participants.

Primary outcome: Median of continuously measured heart rate during sleep.

Secondary outcomes:

- augmentation index (normalized to 75 beats/min),
- heart rate variability metrics (HR standard deviation, min/max, 5th or 95th percentile)
- OSA severity (AHI, oximetry, event duration)
- sleep architecture (percent of each sleep stage during the night)
- Blood pressure
- metabolism (FFA, glucose, insulin).

Blinding:

As this is a double-blind study, above metrics will be calculated for each visit with only knowledge of visit number and not drug/placebo assignment. After these parameters have been derived, the research pharmacy will un-blind the biostatistician ([name]) and PI ([name]) to drug arm assignment to apply appropriate statistical tests, as described below.

Analysis:

For the primary analysis, we will derive summary metrics per night, per participant (i.e. median HR per night). Median heart rate per night will be compared between drug and placebo nights in a paired framework using paired student's T tests. Similar methods will be used to compare secondary outcomes. Some metrics will require additional derivation. For example, heart rate variation will be expressed as coefficients of variation, min/max and lower (5th) and upper (95th) percentiles, and visualized with Poincare plots as performed by collaborators at Johns Hopkins ².

Exploratory Analyses:

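### The Protocol asks whether propranolol and CPAP nights are similar but plans only a difference comparison, with no margin, interval criterion or direction

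*Protocol*

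**What the plan says.** The Protocol's design has three nights per participant: "This protocol compares nocturnal metabolism in treated OSA (CPAP), untreated OSA (NDS), and beta-blocked OSA (NDS) in the same subject". Under Data Analysis and Anticipated Outcomes it states the hypothesis: "We further hypothesize that propranolol will suppress nocturnal FFA and glucose to levels similar to that of CPAP". Section 7 turns this into a secondary outcome: "A secondary outcome is whether CPAP and [NDS + propranolol] are similar, and this will be performed using a similar pairwise comparison".

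The comparisons described just before that sentence are a mixed model for repeated measures ("we will use mixed linear model analysis with experimental group as a fixed factor and subject ID as a random factor") and paired t-tests for measures taken once per visit. The sentence after it adds a one-way ANOVA across the three conditions. All of these look for differences. Neither document defines similar by a margin, a confidence-interval rule or a direction. The FFA sample size rests on propranolol versus placebo alone.

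The SAP (April 2023) describes participants who "temporarily discontinue CPAP for 3 nights prior to each visit". It takes one summary per participant per night, and its primary metric "will be compared between drug and placebo nights in a paired framework". It applies like methods to the secondary outcomes, which include FFA, glucose and insulin. It mentions neither a CPAP night nor a CPAP contrast, and it does not say that the Protocol's outcome was dropped.

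**The concern.** The claim that beta blockade brings FFA and glucose to CPAP-like levels rests on this contrast, and neither possible test result answers it.

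- **Non-significant.** The interval may still include a gap as large as the OSA effect the drug is meant to remove.
- **Significant.** The gap may be trivial, or it may favour propranolol. The second case is not hypothetical. Of the pilot the Protocol says that "FFA levels increased with OSA (CPAP withdrawal), and propranolol abolished this response", yet the propranolol mean is 0.413 − 0.313 = 0.100 mmol/L below CPAP. The plan does not say whether a value below CPAP counts as similar, better or different.

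At stake is the interpretation of one secondary outcome. The propranolol-placebo comparison is not touched by the missing similarity criterion.

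**Working it through.** **The plan's own figure.** The only FFA sample size is for propranolol versus placebo: d = 0.06/0.076 = 0.79, 90% power, alpha 0.05, n = 15. For a paired t-test, n = 15 gives 89.6% power one-sided and 81% two-sided, so the figure reproduces approximately as a one-sided calculation. No figure is given for CPAP versus propranolol.

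**Inputs** (Protocol section 7, sample size; three men)
- Mean FFA ± spread, mmol/L: CPAP 0.413 ± 0.107, placebo 0.447 ± 0.084, propranolol 0.313 ± 0.067. The Protocol labels the ± as an SD only for the placebo-propranolol difference. I assume the condition values are SDs too.
- SD of the placebo-propranolol paired difference: 0.076.
- Target enrolment: 30, as 15 per sex.
- Reference gap: 0.447 − 0.413 = 0.034, the pilot placebo-minus-CPAP difference. This is an illustration, not a proposed margin.

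The sample-size text gives no glucose figures, so only FFA can be illustrated.

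**SD of the CPAP-propranolol difference (not in the documents)**
1. Borrow 0.076 from the placebo-propranolol difference.
2. Or derive a correlation from the pilot and apply it to this contrast:
   - r = (0.084² + 0.067² − 0.076²)/(2 × 0.084 × 0.067) = 0.005769/0.011256 = 0.513
   - SD = √(0.107² + 0.067² − 2 × 0.513 × 0.107 × 0.067) = 0.093
3. Range: the same formula gives 0.126 at r = 0 and 0.055 at r = 0.9.

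**Chance of a non-significant result at a true gap of 0.034.** Two-sided 5% paired t-test on night means. The statistic follows a noncentral t with n − 1 degrees of freedom and noncentrality 0.034 × √n/SD. At n = 30 the critical value is 2.045, and the noncentrality is 2.45 at SD 0.076 and 2.00 at SD 0.093. The 95% CI half-width is 2.045 × SD/√30.

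| SD (n = 30) | P(non-significant) | 95% CI half-width |
|---|---|---|
| 0.055 | 10% | 0.021 |
| 0.076 | 34% | 0.028 |
| 0.093 | 51% | 0.035 |
| 0.126 | 70% | 0.047 |

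At SD 0.093 the half-width exceeds the 0.034 gap itself. At n = 15, the per-sex number, and SD 0.076, the chance is 64% and the half-width 0.042.

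**The opposite case.** If the true gap were the pilot's 0.100 in propranolol's favour, the n = 30 test would be non-significant less than 0.1% of the time at SD 0.093. With no direction stated, that result would read as not similar although the drug had gone beyond the hypothesis.

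**What a margin would deliver.** At n = 30 and a true gap of zero, the chance that the CI lies wholly within ±0.034 is:

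| SD | 95% CI | 90% CI |
|---|---|---|
| 0.076 | 32% | 55% |
| 0.093 | 7% | 25% |

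**The case against.** **The documents never say that non-significance will be read as similarity.** This is correct. A reader might infer that the investigators plan to accept the null, but the text leaves the reading open. The defect is that gap: a question about similarity is posed, and no result is defined as answering it.

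**The later SAP has replaced this outcome.** The SAP's design and analysis cover only drug and placebo nights, so the contrast may no longer be planned. A reader might infer that it was formally dropped. The SAP does not say so, and the Protocol still requires the CPAP night. This limits the weight of the point, and the SAP remedy may be one sentence.

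**The Protocol's mixed model is the larger problem.** Subject is its only random factor, so a reader might infer that the standard error for this contrast is badly understated. That is a separate issue: it would affect drug versus placebo equally, and the SAP compares FFA and glucose through per-night summaries and paired tests. It is not relied on here.

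**A false similarity claim beside a significant drug benefit is unlikely.** On the pilot means this stands. A propranolol mean 0.034 above CPAP is 0.413 + 0.034 = 0.447, the placebo mean, so the drug would have done nothing. A significant result in its favour would then arise at most 2.5% of the time in a two-sided 5% test. A higher joint risk needs a larger OSA effect than the documents report.

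**Conclusion.** The point holds. The stated analysis cannot support the stated conclusion, because a difference test without a margin, interval criterion or direction does not establish similarity. That rests on the text and needs no assumption.

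The size is illustrative. For a true FFA gap of 0.034 mmol/L at n = 30, a non-significant result occurs 34% of the time at SD 0.076 and 51% at SD 0.093, with a range of 10% to 70% for SD 0.055 to 0.126. These figures assume a paired t-test on night means, a borrowed or derived SD, and pilot values from three men.

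The documents do not support extending the point to the propranolol-placebo comparison. The change should be made, but for a secondary outcome only.

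**What to change.** **Protocol, section 7.** Replace the sentence with:

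> Report the mean difference, NDS + propranolol minus CPAP, for FFA and glucose with its 95% CI, from paired per-night means. A non-significant difference will not be interpreted as similarity.

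Per-night means match what the SAP already does for drug versus placebo.

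**Similarity claim.** Make one only if a margin and its direction (two-sided, or not above CPAP) are justified and fixed before any further analysis of the CPAP and propranolol data. Judge it by the matching interval: 90% for two one-sided tests at 0.05, or 95% if so stated. Fixing the margin before the final unblinding is not enough, because the Protocol says "The investigator will unblind the drug assignment after the first 6 completed participants" and already reports pilot FFA for all three conditions. If no margin can be justified, drop the claim.

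**SAP.** Add this contrast if CPAP nights are collected. If they are not, state that the outcome was dropped.

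**Cost.** One sentence in the Protocol and one contrast or sentence in the SAP, with no new data under the three-night design. The downside is that a similarity claim may well prove inconclusive at n = 30, as the interval-within-margin figures above show. That is a reason to make estimation the default.
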